## 4. STATISTICAL ANALYSES

### 4.1. General Considerations

#### 4.1.1. General Methodology

Enrolled participants who prematurely withdraw from study will not be replaced.

In the case of the wrong stratification assigned at the time of randomization, the analyses will be performed based on the actual stratum per data collected in the eCRF.

Confidence intervals (CIs) will use 95% confidence levels, unless otherwise specified.

In general, CIs for proportions will be calculated CCI

██████████. All continuous data will be summarized using descriptive statistics (n, mean, standard deviation [SD], median, minimum and maximum) and categorical data will be summarized using the number and percentage of participants in each category.

GMCs of antibody concentrations and related CIs will be obtained by computing average and CI using the t-distribution on log10-transformed data, and subsequently back-transforming these to the original scale.

#### 4.1.2. Definitions

- For all endpoints, the baseline value will be the latest pre-dose assessment with a non-missing value. If sample collection time is not recorded, Day 1 assessments are assumed to be taken prior to first dose and used as baseline.
- A seronegative participant will be defined as a participant whose antibody concentration is below the cut-off value of the assay (CLIA anti-HBs titer  $< 6.2 \text{ mIU/mL}$ ).
- A seropositive participant is a participant whose antibody concentration is greater than or equal to the cut-off value of the assay (CLIA anti-HBs titer  $\geq 6.2 \text{ mIU/mL}$ ).
- Seroprotection threshold is CLIA anti-HBs titer  $> 10 \text{ mIU/mL}$ .
- Seroconversion threshold is CLIA anti-HBs titer  $> 6.2 \text{ mIU/mL}$ .
- CCI [REDACTED]

### 4.2. Primary Endpoints Analyses

#### 4.2.1. Analysis of safety planned in the protocol

The primary endpoints will be based on the reactogenicity and safety objectives and will be performed on the ES. Below the follow-up period for solicited AEs is intended for Dose 1 and Dose 2 only and not Dose 3.

- The percentage of participants reporting at least one solicited adverse event (AE), at least one solicited administration site AE, and at least one solicited systemic AE during the 14-day follow-up period (i.e., the day of vaccination and 13 subsequent days) will be tabulated for each group after each dose and overall. For solicited AEs, percentages will be computed based on the total number of solicited symptoms screens completed.
- The number and percentage of participants reporting each individual solicited AE during the 14-day follow up period post-vaccination (i.e., the day of vaccination and 13 subsequent days) will be tabulated with exact 95% CI and descriptive statistics for each group, after each dose and overall.
- The number and percentage of participants reporting each individual solicited administration site AE (any grade, Grade 3 and resulting in medically attended visit) and solicited systemic AE (any grade, Grade 3 and resulting in medically attended visit) during the 14-day follow-up period (i.e. the day of vaccination and 13 subsequent days) will be tabulated for each group, after each dose and overall.

- The number and percentage of participants with each solicited administration site event and separately, solicited systemic event (any grade and grade 3) within the 14-day follow up period will be represented graphically with a bar plot for each group and after each dose.
- The duration of each individual solicited AE during the 14-day follow-up period will be tabulated using descriptive statistics (mean, minimum, Q1, median, Q3, maximum). The same computations will be done for Grade 3 solicited events. This analysis will be done for each group after each dose.
- The number and percentage of participants reporting each individual unsolicited AE category during the 31-day follow up period post-vaccination (i.e., the day of vaccination and 30 subsequent days) will be tabulated with exact 95% CI by event category (e.g., all, grade 3, related, grade 3 related, serious adverse events [SAEs], fatal etc.) for each group, after each dose and overall. Percentages will be computed based on the total number of exposed participants. Participants not reporting an AE will be considered as not having experienced any AE.
- The number and percentage of participants with any unsolicited AEs during the 31-day follow-up period (i.e. the day of vaccination and 30 subsequent days) will be tabulated with exact 95% CI by study group and categorized by Medical Dictionary for Regulatory Activities (MedDRA) system organ class (SOC) and preferred term (PT) (i.e. the table will be grouped by SOC and then preferred terms will be included within each group). Similar tabulation will be done for Grade 3 unsolicited AEs, for any causally related unsolicited AEs, for Grade 3 causally related unsolicited AEs and for unsolicited AEs resulting in a medically attended visit and at least one solicited or unsolicited adverse event excluding SAE. The verbatim reports of unsolicited AEs will be reviewed by a physician and the signs and symptoms will be coded according to the MedDRA Dictionary for Adverse Reaction Terminology. Every verbatim term will be matched with the appropriate preferred term. This will be done by group, after each dose and overall. The summary tables without SOC and PT information will be also produced for the follow-up period lasting until study end.
- The number and percentage of participants reporting each individual unsolicited AE during the 31-day follow-up period (i.e. the day of vaccination and 30 subsequent days) will be tabulated and ranked by MedDRA PT with the most common appearing first. This analysis will be done for each group after each dose and overall.
- The number and percentage of participants with at least one solicited or unsolicited medically attended event (MAE) reported any time between the day of vaccination (Day 1) and the end of the study period post vaccination (up to Day 61 for main analysis, up to Day 361 for final analysis) will be classified by MedDRA SOC and PT and tabulated with exact 95% CI. This analysis will be done by group.
- The number and percentage of participants with at least one serious adverse event (SAE) reported any time between the day of vaccination (Day 1) and the end of the study period post vaccination (up to Day 61 for main analysis, up to Day 361 for final analysis) will be classified by MedDRA SOC and PT and tabulated with exact 95% CI. This analysis will be done by group. The same tabulation will be presented for causally related SAEs, fatal SAEs and causally related fatal SAEs.

- The number and percentage of participants with at least one potential immune-mediated disease (pIMD) (selection defined by GSK list of terms AND/OR investigator tick box) reported any time between the day of vaccination (Day 1) and the end of the study period post-vaccination (up to Day 61 for main analysis, up to Day 361 for final analysis) will be classified by MedDRA SOC and PT and tabulated with exact 95% CI. This analysis will be done by group. The same tabulation will be presented for causally related pIMDs.
- The number and percentage of participants reporting each individual pIMD, SAE, or MAE that occurred in the study up to study end/database freeze (DBF) prior to the main analysis will be tabulated and categorized by MedDRA SOC and PT with exact 95% CIs, after each dose and overall. This analysis will be done by group. Note: different groups and doses will have different amounts of follow up time.
- All SAEs/MAEs/pIMD will be described in detail in a tabular listing.
- All AEs/SAEs leading to study/intervention discontinuation from dose 1 up to study end/DBF for main analysis will be tabulated and described in detail in a tabular listing.
- All participants taking concurrent medication/vaccines will be described in a detailed listing.
- For each group and for each hematology and biochemistry parameter, as reported in Table 22 of the study protocol:
  - Comparison of changes since baseline i.e., summary of absolute and relative differences for each parameter by timepoint and by group will be tabulated with descriptive statistics.
  - The number and percentage of participants having hematology and biochemistry results below or above the central laboratory defined normal ranges will be tabulated by timepoint [pre-vaccination (Day1), post-dose 1 (Day 8 and Day 31), post-dose 2 (Day 38 and Day 61)]. This will be done for each group and overall.
  - The summary of grading post-study intervention administration will be tabulated vs. baseline. Grades will be based on the FDA Guidance for Industry “Toxicity Grading Scale for Healthy Adults and Adolescent Volunteers Enrolled in Preventive Vaccine Clinical Trials” (see Section 10.2.1 of the protocol). The laboratory parameters not included in the FDA Toxicity Grading Scale will not be graded.
- Compliance in completing solicited events information will be tabulated after each dose and overall. The number of completed eDiary days in the solicited period for a participant will be summarized by study group using frequency table. Refer to Section 6.2 for more information.
- Pregnancy and pregnancy outcomes will be listed (if applicable).

- The percentage of participants using concomitant medication (any medication, any antipyretic, and any antipyretic taken prophylactically, respectively) during the 14-day follow-up period (i.e., the day of vaccination and 13 subsequent days) and during the 31-day follow-up period (i.e., the day of vaccination and 30 subsequent days) will be summarized by group after each dose and overall.
- Number and percentage of participants meeting each holding rule will be tabulated with exact 95% CI. This analysis will be done by group and for each dose. Furthermore, it will be done separately by cohort 1, cohort 2 as well as the two together (cohort 1 and cohort 2 combined).

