3. OBJECTIVES AND ENDPOINTS

Table 3 Study objectives and endpoints

Objectives	Endpoints	Primary
To evaluate the reactogenicity and safety in all study groups.	
 Percentage of participants with solicited administration site and systemic AEs within 14 days (Day 1 till Day 14) after Dose 1 and Dose 2. Duration of solicited AEs (administration site and systemic) after Dose 1 and Dose 2. Percentage of participants with any unsolicited AEs within 31 days (Day 1 till Day 31) after Dose 1 and Dose 2. Percentage of participants with SAEs, MAEs and AEs leading to study withdrawal throughout the entire study period. Percentage of participants with pIMDs throughout the entire study period. The absolute values and changes in hematology and biochemistry parameters post-Dose 1 (Day 8 and Day 31) and post-Dose 2 (Day 38 and Day 61) from baseline (pre-vaccination, Day 1). 	

CONFIDENTIAL

215301 (EARLY-CLINRES-017)

Protocol Amendment 4 Final

Objectives	Endpoints
	
 Percentage of participants with abnormal laboratory parameter values at pre-vaccination (Day 1), post-Dose 1 (Day 8 and Day 31) and post-Dose 2 (Day 38 and Day 61).
	Secondary
To evaluate the humoral immune response in all study groups.	
 GMC of Anti-HBs Ab concentrations at Day 1, Day 31, Day 61 and Day 361. Anti-HBs seroconversion and seroprotection rates at Day 31, Day 61 and Day 361.
	Tertiary
CC1	
To evaluate the cell-mediated immune response induced in all study groups.	
 Frequency of HBsAg-specific CD4+/CD8+ T-cells per 10^6 CD4+/CD8+ T-cells producing at least 2 activation markers including at least 1 cytokine among IFN-γ, IL-2, TNF-α, IL-13, IL-17, 4-1BB and/or CD40L at Day 1, Day 8, Day 31, Day 38, Day 61 and Day 361. Frequency of plasmablasts, T Follicular Helper cells (TFH) and memory B-cells (flow cytometry) at Day 1, Day 8, Day 31, Day 38 and Day 61, in a subset of participants.
CC1	
	
 Frequency of HBsAg-specific memory B-cells (ELISPOT) at Day 1, Day 31, Day 61 and Day 361.
CC1	

AE = adverse event; **SAE** = serious adverse event; **MAE** = medically attended event; **pIMD** = potential immune-mediated disorder; **GMC** = geometric mean concentration; **HBs** = Hepatitis B surface antigen; **Ab** = antibody; **CC1** [REDACTED]

[figure not shown]
CC1 [REDACTED]

CC1 [REDACTED]

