9.3.1. Primary endpoints analyses

The analysis of the primary objective will be performed on the Exposed Set (ES).

Endpoint description	Analysis set	Statistical analysis methods
Reactogenicity and Safety	Exposed	
Descriptive statistics:
 
 Percentage of participants with solicited administration site and systemic AEs within 14 days (Day 1 till Day 14) and severity grading will be tabulated with exact 95% CI for each group after Dose 1 and Dose 2 of the study intervention and overall. Descriptive statistics of duration of solicited AEs (administration site and systemic) will be tabulated for each group after Dose 1 and Dose 2 of the study intervention and overall. Percentage of participants with any unsolicited AEs within 31 days (Day 1 till Day 31) and severity grading will be tabulated with exact 95% CI for each group after Dose 1 and Dose 2 of the study intervention and overall. Percentage of participants with SAEs, related SAEs, MAEs and AEs leading to study withdrawal throughout the entire study period will be tabulated with exact 95% CI for each group. Percentage of participants with pIMDs throughout the entire study period will be tabulated with exact 95% CI for each group. Descriptive statistics of the absolute values and changes in hematology and biochemical parameters from baseline at each protocol specified timepoints will be tabulated for each group. Percentage of participants with abnormal laboratory parameter values will be tabulated with exact 95% CI for each group pre-vaccination, after Dose 1 and after Dose 2 of the study intervention and overall.

AE = adverse event; **CI** = confidence interval; **SAE** = serious adverse event; **MAE** = medically attended event;

pIMD = potential immune-mediated disorder.

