10.3.3. **Solicited events**

Solicited events are predefined administration site events and systemic events for which the participant is specifically questioned, and which are noted by the participant in their eDiary.

a. **Solicited administration site events**

The following administration site events will be solicited:

Table 23 Solicited administration site events

Pain at administration site
Redness at administration site
Swelling at administration site

b. **Solicited systemic events**

The following systemic events will be solicited:

Table 24 Solicited systemic events

Fever
Fatigue
Myalgia
Arthralgia
Headache
Chills
Malaise
Loss of appetite
Nausea
Vomiting
Diarrhea

Note: participants will be instructed to measure and record the oral temperature in the evening. If additional temperature measurements are taken at other times of the day, participants will be instructed to record the highest temperature in the eDiary. Other options for temperature records include the axilla, ear canal and forehead; but oral temperature remains the preferred option.

10.3.4. **Unsolicited AEs**

An unsolicited AE is an AE that was either not included in the list of solicited events or could be included in the list of solicited events but with an onset outside the specified period of follow-up for solicited events. Unsolicited events must have been spontaneously communicated by a participant who has signed the informed consent. Unsolicited AEs include both serious and non-serious AEs.

Potential unsolicited AEs may be medically attended (i.e., symptoms or illnesses requiring a hospitalization, or an emergency room visit, or visit to/by a health care provider). The participants will be instructed to contact the site as soon as possible to report medically attended event(s), as well as any events that, though not medically attended, are of participant's concern. Detailed information about reported unsolicited AEs will be collected by qualified site personnel and documented in the participant's records.

Unsolicited AEs that are not medically attended or perceived as a concern by the participant will be collected during an interview with the participants and by review of available medical records at the next visit.

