10.3.8.1. Time period for collecting and recording AEs, SAEs, MAEs, pIMDs and pregnancies

All solicited events that occur up to 14 days following administration of Dose 1 and Dose 2 of study intervention (Day 1 to Day 14 and Day 31 to Day 44, respectively) must be recorded into the eDiary, irrespective of intensity. All other AEs occurring within 31 days following Dose 1 and Dose 2 of study intervention administration should be recorded onto the appropriate section of the eCRF, irrespective of their intensity or whether or not they are considered related to the study intervention.

The time period for collecting and recording of SAEs, MAEs, pIMDs, and pregnancies will begin at the first receipt of study interventions and will continue throughout the whole study period.

All AEs/SAEs leading to withdrawal from the study will be collected and recorded from the time of the first receipt of study intervention until the participant is discharged from the study. SAEs related to study participation or to a concurrent GSK medication/vaccine will be collected from the time consent is obtained until the participant is discharged from the study.

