### 6.3.3.6. Duration of events

The duration of an event with a start and end date will be the difference between the start and end date plus one day, i.e. an event that starts on 3 March 2018 and ends on 12 March 2018 has a duration of 10 days.

The duration of solicited events will be calculated as the sum of the individual days with the AE reported at grade 1 or higher during the solicited event period as well as time between the first and the last day of symptoms.

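### The SAP's symptom-day count for solicited AEs stops at Day 14, although the protocol's duration endpoint has no day limit and the eDiary continues; whether the first-to-last span also stops is not stated

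*SAP*

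**What the plan says.** **Protocol.** Section 3 (Table 3) lists two neighbouring primary endpoints. Incidence carries a window: "Percentage of participants with solicited administration site and systemic AEs within 14 days (Day 1 till Day 14) after Dose 1 and Dose 2". Duration does not: "Duration of solicited AEs (administration site and systemic) after Dose 1 and Dose 2". Section 9.3.1 repeats the contrast, and its duration entry reads "Descriptive statistics of duration of solicited AEs (administration site and systemic) will be tabulated for each group after Dose 1 and Dose 2", again with no day limit. On recording, section 10.3.8.1 covers "All solicited events that occur up to 14 days following administration of Dose 1 and Dose 2 of study intervention" and then gives the ranges Days 1-14 and Days 31-44. The Schedule of Activities (section 1.3) also shows recording of solicited events for Days 1-14. Section 10.3.4 treats a symptom as unsolicited if it "could be included in the list of solicited events but with an onset outside the specified period of follow-up for solicited events", so onset is the dividing line.

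**SAP.** Section 4.2.1 plans the table: "The duration of each individual solicited AE during the 14-day follow-up period will be tabulated using descriptive statistics". It repeats the computation for Grade 3 events. Section 6.3.3.6 names two measures of solicited duration. The first is a count of symptom-days: "sum of the individual days with the AE reported at grade 1 or higher during the solicited event period". The second is a span, which the same sentence adds in these terms: "as well as time between the first and the last day of symptoms". Section 6.2.1 has participants continue diary entries for any symptom still present after the 14 days, until its intensity is none. It describes Days 15-31 as lying beyond the solicited follow-up period. Section 6.2.2 summarises diary completion for those days. Section 6.3.3.8 keeps continuing solicited events out of the unsolicited summaries. Section 4.8 declares no change to the protocol's analyses.

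**The concern.** Duration is a primary safety endpoint in a dose-escalation study whose protocol (sections 2.3.1 and 4.4) names higher reactogenicity of the 100 µg formulation as a potential risk. Long reactions are what a duration endpoint should show. The SAP collects diary days after Day 14 and reports how complete they are, yet its symptom-day rule leaves them out. No planned summary of duration clearly uses them.

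Any shortening would fall on the groups with the most persistent reactions and would be strongest for late onsets. There is also a practical problem. Sections 4.2.1 and 6.3.3.6 allow two programmers to build different tables: they can choose either measure, and can cut the span at Day 14 or not.

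**Working it through.** **Inputs.** The solicited period is Days 1-14 after each dose (SAP 4.2.1). Days 15-31 lie outside it (SAP 6.2.1). The general rule for a dated event is end minus start plus one day (SAP 6.3.3.6). Group size is 23 to 30 (SAP 5). The Dose 1 to Dose 2 interval is 21-42 days (Protocol Table 2). Neither document gives any event durations, so the event patterns below are assumptions.

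**1. The SAP's own example.** For 3 to 12 March, 12 - 3 + 1 = 10 days, as the SAP states.

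**2. Limit on the symptom-day count.** An unbroken event with onset on Day k and end on Day e counts min(e, 14) - k + 1 days. The most it can count is 14 - k + 1 = 15 - k: 14 days for onset on Day 1, 10 for Day 5, 5 for Day 10 and 1 for Day 14.

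| Event | Counted to Day 14 | All recorded days |
|---|---|---|
| Days 2-5 | 4 | 4 |
| Days 10-20 | 5 | 11 |
| Days 14-20 | 1 | 7 |
| Days 1-20 | 14 | 20 |
| Days 1-31 | 14 | 31 |

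For unbroken events, the first-to-last span with the added day gives the same pairs if it is also cut. If it is not cut, it gives the right-hand column.

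**3. Effect on the summary statistics (assumed data).**

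- Ten events, of which m run Days 10-20 and the rest last 2 days. The cut mean is (2(10 - m) + 5m)/10 and the uncut mean is (2(10 - m) + 11m)/10. For m = 1, 2, 3 this gives 2.3 against 2.9, 2.6 against 3.8, and 2.9 against 4.7. The maximum is 5 against 11 and the median is 2 throughout. The third quartile stays at 2 for m = 1 or 2. For m = 3 it moves from 11 to 5 when cut (nearest rank), or from 8.75 to 4.25 (linear interpolation).
- Twenty-three reporters, 21 with 3-day events and 2 with events on Days 2-20. The cut mean is (63 + 26)/23 = 3.87 and the uncut mean is (63 + 38)/23 = 4.39. The maximum is 13 against 19 and the median is 3 in both.
- One event on Days 10-20 loses 6 days, so the mean over n events falls by 6/n: 0.60 for n = 10, 0.26 for n = 23 and 0.20 for n = 30.

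**4. Overlap with Dose 2 if later days are used.** At a 21-day interval Dose 2 falls on Day 22, so Days 22-31 overlap: 10 days. At 25 days the overlap is 6, at 30 days it is 1, and from 31 days it is none. These counts cover Days 15-31 only. Diary entries can run longer, so a longer-lasting symptom can overlap at longer intervals too.

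**The case against.** A reader might infer that the SAP cuts every duration measure at Day 14 and so departs from the protocol without declaring it. The documents do not support that, for three reasons.

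First, SAP 6.3.3.6 also names the first-to-last span and puts no limit on it. Second, the 14-day phrase in SAP 4.2.1 can qualify the event rather than its length. Neighbouring bullets use the same phrase to select events, and on that reading an uncut span is consistent with the continuing diary. Third, the protocol itself sets the recording of solicited events at Days 1-14. Only the SAP describes entries after that, in an appendix added by SAP Amendment 3. A count over Days 1-14 can thus be read as matching the protocol's recording window and may have been intended. Section 6.3.3.8 of the SAP keeps continuing events from being counted as unsolicited; it does not say that their length is lost.

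It is also fair to say that no passage shows how often reactions pass Day 14, so the examples illustrate the mechanism and do not predict its size.

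These points limit the finding without removing it. None of them changes the wording of the symptom-day rule, which is confined to the solicited period, and the SAP's own text places Days 15-31 outside that period.

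**Conclusion.** By its stated rule, the symptom-day count understates any solicited event that passes Day 14, by the number of symptom-days after Day 14. For the span, and for the choice of measure in the 4.2.1 table, the SAP is unresolved. Truncation of every measure and a definite protocol deviation are not shown.

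If events do pass Day 14, the mean and maximum are mainly affected. The median and third quartile move little unless many events persist. The actual size is unknown. Grade 3 durations share the problem, but solicited-AE incidence and Grade 3 percentages do not. The solicited-event holding rules use onset within Days 1-7 and Grade 3 lasting at least 48 hours, so they are unaffected. The analyses are descriptive, so no test result changes.

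The point should be corrected, because the endpoint is primary and the data are already being collected. Confidence is moderate, since the intended reading of SAP 4.2.1 and what was actually programmed cannot be seen from the documents.

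**What to change.** In SAP 4.2.1 and 6.3.3.6:

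- State that the 14-day period selects events by onset on Days 1-14.
- Report both measures that 6.3.3.6 names as separately labelled rows, each using the diary days after Day 14: symptom-days, and first-to-last day plus one day.
- Do the same for Grade 3 days.
- Attribute each event to the dose after which it started, as SAP 6.3.1 provides.
- Give the number of events still ongoing at the next dose or at the last diary entry, and mark their durations as lower bounds.

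What to declare depends on what was programmed. The rationale for Protocol Amendment 4 refers to immunogenicity results from the Day 61 main analysis, which by plan also covers safety, so that analysis appears to have been run. If it used the cut version, keep that version for comparison, label the uncut rows as added later, and describe the restriction in SAP 4.8 and the CSR. If the span was already programmed uncut, it is enough to say so.

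The cost is SAP wording, a small change to derivation code and some extra table rows. The drawback is that some post-Dose 1 diary days can overlap Dose 2: for Days 15-31, up to 10 days at the shortest allowed interval. This is why events ongoing at the next dose should be counted and flagged.
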